4.2.2. Analysis of Secondary Endpoints

4.2.2.1. Transfusion Burden

For the LTB and HTB strata only, the total RBC units transfused and % reduction from baseline will be summarized for each of the following 8-week study intervals: Week 1 to 8 (Rel Day 2 to 57), Week 9 to 16 (Rel Day 58 to 113), Week 17 to 24 (Rel Day 114 to 169), Week 25 to 32 (Rel Day 170 to 225), Week 33 to 40 (Rel Day 226 to 281), Week 41 to 48 (Rel Day 282 to 337).

% reduction from baseline in RBC transfusion burden is defined as

$$-100 \times \frac{\text{Total RBC Units Transfused During Interval}}{\text{Baseline RBC Units Transfused Per 8 Weeks}}$$

Patients who have discontinued treatment prior to completing the specified interval will be excluded from the analysis.

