Coagulation parameters ^g	X			X						X			X												X	X	
Serum Pregnancy Test ^j	X																										
Serum Erythropoietin	X																										
Serum Virology ^g	X																										

Forma Therapeutics, Inc. Clinical Study Protocol 4202-ONC-203

Assessments	Screen		Primary treatment period												Extension treatment period											Safety follow- up visit
Study Day/Week(s):	D-42	W1D1	W2 D1	W4 D1	W6 D1	W8 D1	W10 D1	W12 D1	W14 D1	W16 D1	W20 D1	W22 D1	W24 D1	W26 D1	W28 D1	W30 D1	W32 D1	W34 D1	W36 D1	W38 D1	W40 D1	W42 D1	W44 D1	W46 D1	W48 D1	W52 D1
	to -1		(±3 D)	(±3 D)	(±3 D)	(±3 D)	(±3 D)	(±3 D)	(±3 D)	(±3 D)	(±3 D)	(±3 D)	(±3 D)	(±3 D)	(±3 D)	(±3 D)	(±3 D)	(±3 D)	(±3 D)	(±3 D)	(±3 D)	(±3 D)	(±3 D)	(±3 D)	(±3 D)	(±3 D)
Transfusion Data Collection and Assessment		Assess and record on ongoing basis until end of treatment visit or 8 weeks after last dose of etavopivat, whichever comes first. Clinical staff should confirm if any transfusions were received by the patient (including any at outside local institutions in between study visits).																								
PROMIS Fatigue Scale	X	X		X		X		X		X	X		X				X				X				X	X
The QUALMS	X	X		X		X		X		X	X		X				X				X				X	X
MDS Baseline Assessment (IPSS-R) ^k	X																									
MDS Response Assessment ¹										X			X m												X	X
Exploratory Studies n	X	X		X						X	X		X				X				X				X	
PD Sampling °		X	X	X																					X	X
PK Sampling ^p		X	X	X									X												X	
Study Drug Administration		X										Dai	ly throu	ghout ti	reatmen	t period										
Survival q												Q 3	months	after E	nd of Ti	rial visit					•				•	

Abbreviations: BMI = body mass index; D = day; ECOG PS = Eastern Cooperative Oncology Group performance status; ECG = electrocardiogram; ESA = Erythropoiesis-stimulating agent; Hb = hemoglobin; ICF = informed consent form; IPSS-R = International Prognostic Scoring System-Revised; MDS = myelodysplastic syndromes; PK/PD = pharmacokinetics/pharmacodynamics; PROMIS = Patient-Reported Outcomes Measurement Information System; RBC = red blood cell; The QUALMS = The Quality of Life in Myelodysplasia Scale; W = week.

Note: Study visits after W1D1 must be conducted within ± 3 days of the scheduled visit. For the purposes of assessments and analyses in this study, 4 weeks = 1 month.

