4.2.1. Analysis of Primary Endpoints

4.2.1.1. HI-E Response and MDS assessments

The proportion of patients with HI-E response ≥ 8 weeks within 24 weeks of etavopivat treatment will be analyzed across the pooled strata and within each stratum. Patients will be considered responders if they satisfy HI-E criteria during any continuous ≥ 8 -week treatment interval up to W24D1.

HI-E criteria are defined based on the patient's transfusion history stratum at D1:

NTD: A patient is considered a responder where at least one continuous interval ≥ 8 weeks occurs where all of the following criteria are met:

- Hb is increased by ≥ 1.5 g/dL relative to baseline at 2 or more consecutive visits
- Relapse date (date of first Hb measurement with < 1.5 g/dL change from baseline following the qualifying increase) occurs at least 8-weeks after the first incidence of qualifying Hb increase
- Patient is free of RBC transfusions

LTB: A patient is considered a responder if they are free of RBC transfusions over any continuous 8-week period.

HTB: A patient is considered a responder if they have a $\geq 50\%$ reduction in RBC transfusion burden relative to baseline RBC transfusion burden per 8 weeks over any continuous 8-week period.

Percent reduction in RBC transfusion burden is calculated for all rolling 56-day intervals in the 24-week primary treatment period (i.e. Days 2-57, Days 3-58,..., Days 113-168) as

$$-100 \times \frac{RBC \text{ units transfused in 56 day interval} - \text{Baseline RBC transfusion burden per 8 weeks}}{\text{Baseline RBC transfusion burden per 8 weeks}}$$

The numerator for the response rate will be the total number of responders (summed across all baseline transfusion categories). The denominator will be the number of patients in the EES.

MDS baseline assessment including the score based on Revised International Prognostic Scoring System (IPSS-R) for MDS and MDS response assessment will be presented in data listings.

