5.3. Additional Changes

No patients were anticipated to enter the optional prolonged treatment period. Therefore, related information such as treatment exposure definition and schedule of events are not applicable and are not included in this SAP.

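### SAP 4.2.2.1: for completers, the Week 41–48 transfusion interval ends 4–10 days after recording stops; separately, the Week 24 period has three different end days

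*SAP*

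**What the plan says.** **Secondary summary.** For LTB and HTB patients, SAP 4.2.2.1 tabulates RBC units and percent reduction from baseline in consecutive 56-day blocks starting at Day 2. The third is "Week 17 to 24 (Rel Day 114 to 169" and the sixth "Week 41 to 48 (Rel Day 282 to 337". It adds: "Patients who have discontinued treatment prior to completing the specified interval will be excluded from the analysis".

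**Recording period.** Protocol Table 1-1 gives the rule for transfusion data: "Assess and record on ongoing basis until end of treatment visit or 8 weeks after last dose of etavopivat, whichever comes first". Protocol 8.2.2 describes recording throughout the study but defers to the same schedule tables. The end-of-treatment visit is W48D1 for a completer, and for an early stopper it is held at discontinuation (Protocol 7.2.1). SAP Table 3 puts W48D1 at Day 330, window 327–333. SAP 5.3 states: "No patients were anticipated to enter the optional prolonged treatment period".

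**Primary endpoint.** SAP 4.2.1.1 requires HI-E criteria to be met "during any continuous ≥ 8 -week treatment interval up to W24D1". SAP Table 3 puts W24D1 at Day 162, window 159–165. For the HTB percent reduction, the same section lists the rolling windows as "Days 2-57, Days 3-58,..., Days 113-168".

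**The concern.** A transfusion-burden interval is interpretable only if transfusions were recorded throughout it. Transfusions are event records, so a day outside the recording period contributes no units to a sum, just like a day without a transfusion. A window that overruns recording therefore leans towards apparent benefit unless the analysis requires complete observation or adjusts for observed time.

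At stake in 4.2.2.1 is the last row of one of the few efficacy summaries kept in this shortened SAP. In 4.2.1.1 the question is whether two programmers would classify a borderline patient the same way, and whether an HTB patient who stops at about Week 24 could be judged on a partly unrecorded window.

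**Working it through.** **1. Study-day grid.** Day of Week k Day 1 = 7 × (k − 1) + 1.
- W24D1: 7 × 23 + 1 = 162, as in SAP Table 3.
- W48D1: 7 × 47 + 1 = 330, as in SAP Table 3.
- W52D1: 7 × 51 + 1 = 358, which is 330 + 28. This matches the 28-day off-drug period in Protocol 4.1, so the schedule has drug stopping at about Day 330.

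**2. SAP 4.2.2.1 intervals.** Length = end − start + 1. The six intervals (2–57, 58–113, 114–169, 170–225, 226–281, 282–337) are each 56 days. The overrun comes from the labels: W48D1 opens Week 48, so 47 weeks have elapsed, whereas six 56-day blocks from Day 2 cover 48 weeks.

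**3. Overrun of the last interval.** Unrecorded days = 337 − visit day; recorded days = visit day − 282 + 1.

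| W48D1 visit | Recorded days | Unrecorded days | Share of 56 |
|---|---|---|---|
| Day 327 | 46 | 10 | 17.9% |
| Day 330 | 49 | 7 | 12.5% |
| Day 333 | 52 | 4 | 7.1% |

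**4. What the exclusion rule does.**
- *Literal reading.* Protocol 7.2.1 treats permanently stopping study drug as discontinuation. A completer who stops at W48D1 has done so before Day 337 and is excluded, leaving the row empty or nearly so.
- *Completers kept.* With unchanged, evenly spread use, expected recorded units are baseline × recorded days / 56. The apparent reduction equals the unrecorded share, 7.1% to 17.9%. At an illustrative 4 units per 8 weeks (the HTB entry minimum of 8 units in 16 weeks, averaged), the missed amount is 4 × 4/56 = 0.29 to 4 × 10/56 = 0.71 units.

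These percentages use the change-from-baseline form printed in 4.2.1.1. The formula printed in 4.2.2.1 omits the subtraction of baseline and would give −100 for unchanged, fully recorded use. That needs its own correction; the intended calculation is assumed here.

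**5. Week 24.** There are three end days: Day 162 (W24D1), Day 168 (last rolling window) and Day 169 (third fixed interval).
- *Patients entering the extension.* Recording continues past Week 24, so Days 163–169 are observed and no days are missing.
- *HTB patients whose end-of-treatment visit falls at about W24D1.* Unrecorded days to Day 168 are 168 − 159 = 9, 168 − 162 = 6 or 168 − 165 = 3. Window starts run from Day 2 to Day 113, giving 112 windows; 9, 6 or 3 of them end after the visit. The last window then has 47, 50 or 53 recorded days.

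Such a patient remains in the Efficacy Evaluable Set, having completed the Week 24 visit (SAP 2.1). SAP 4.2.1.1 has no counterpart to the 4.2.2.1 exclusion rule.

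**The case against.** The strongest reply has four parts.

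- **W24D1 does not end recording.** Correct. A reader might infer from the Day 168 windows that the primary endpoint generally counts unobserved days as transfusion-free. The documents do not support that: Protocol 4.3.1 continues treatment through a 24-week extension, and Table 1-1 keeps recording until the end-of-treatment visit.
- **LTB patients are not exposed in the way one might suppose.** Also correct. It is tempting to say that an LTB patient last transfused on Day 112 who stops on Day 162 becomes a responder on 50 observed days. But 4.2.1.1 asks for an 8-week treatment interval up to W24D1, and 50 days is not 8 weeks. The rolling grid is printed only for the percent-reduction calculation, which is the HTB criterion. For HTB patients the same general sentence pulls against the explicit grid to Day 168, and the SAP does not say which governs.
- **The SAP nowhere says unrecorded days count as zero, and SAP 3.9 makes no substitution for missing data.** True as to wording, so the zero count is an inference. But no substitution is needed to produce it: summing recorded units over an incompletely recorded window gives that result. The alternative, excluding completers, leaves the last row without usable data.
- **The consequences are small.** Largely accepted. Week 41–48 is one of six intervals in an untested summary, for two strata, in an abbreviated report after the study ended early (SAP 1.1).

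**Conclusion.** The Week 41–48 interval is wrong as written. For a completer seen within the W48D1 window, 4–10 of 56 days (7–18%) fall after recording stops. The row is then either empty or, on average, biased towards a reduction of about 7–18%. This assumes that completers stop at W48D1, that nobody enters prolonged treatment (which SAP 5.3 anticipates), that use is evenly spread and unchanged, and that percent reduction is computed as a change from baseline. The number of patients reaching Week 48 is not given.

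At Week 24 the firm finding is an inconsistent end day: 162, 168 or 169. The missing completeness rule exposes only HTB patients whose end-of-treatment visit falls at about Week 24, with 3–9 unrecorded days in at most 9 of 112 windows. The documents do not say how many such patients there are. At the planned 45 evaluable patients, one reclassified responder would move the rate by 1/45 = 2.2 percentage points. A change to the primary result is possible but not shown.

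**What to change.** **SAP 4.2.2.1.** End the last interval at the end-of-treatment (W48D1) visit. Scale units as units × 56 / days observed; for example, 3.5 units in 49 days becomes 3.5 × 56/49 = 4. State that a patient completing W48D1 is not excluded as having discontinued.

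**SAP 4.2.1.1.** Name one Week 24 end day and use it in both sections. Day 169 would leave the 4.2.2.1 intervals as they are and add one rolling window (Days 114–169); Day 168 would need the fixed intervals realigned. Reword the limit at W24D1 to match. Count a 56-day window only if it ends on or before the patient's last transfusion-assessment date. Do not cap continuing patients at their own W24D1 visit date: that would discard observed days and could remove true responders.

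**Cost.** SAP wording and programming, with no new data collection. A borderline responder who stops at Week 24 may be lost. Scaling assumes that use in the unrecorded days resembles use in the recorded ones, a modest extrapolation when 46–52 of 56 days are observed.

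### SAP 4.2.2.1 leaves the baseline subtraction out of its percent-reduction formula, so every defined value is 100 percentage points too low

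*SAP*

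**What the plan says.** Reduction in RBC transfusions in LTB and HTB patients is among the secondary efficacy endpoints kept in the abbreviated SAP (SAP 1.1.1.2). SAP 4.2.2.1 reports two summaries for those strata in each of six consecutive 8-week intervals: total units, and percent reduction from baseline. For the second, % "reduction from baseline in RBC transfusion burden is defined as" -100 multiplied by a fraction. Its numerator is "Total RBC Units Transfused During Interval" and its denominator is "Baseline RBC Units Transfused Per 8 Weeks". Nothing is subtracted in the numerator.

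SAP 4.2.1.1, on the primary endpoint, has its own formula: "Percent reduction in RBC transfusion burden is calculated for all rolling 56-day intervals", as -100 times (interval units minus baseline burden per 8 weeks) divided by baseline burden per 8 weeks. It serves the HTB response rule, a reduction of at least 50%: "reduction in RBC transfusion burden relative to baseline RBC transfusion burden per 8 weeks over any continuous 8-week period".

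SAP 3.3 gives one definition of baseline burden per 8 weeks: units summed over the 8 weeks up to pre-dose Day 1. SAP 5.1 says no clarifications are needed, and SAP 5.2 does not list the difference between the two formulas as a change.

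**The concern.** One SAP gives two formulas for percent reduction in transfusion burden, and they differ only in whether baseline is subtracted. The leading -100 makes sense only with the subtraction, because it turns a negative change into a positive reduction. Without it, the expression cannot measure a reduction.

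If 4.2.2.1 is programmed as written, the table will report 0% reduction for the best possible outcome and can never show a positive figure. SAP 5.2 drops most of the protocol's other secondary efficacy endpoints, so this is one of the few efficacy tables left in the report. In some rows it would also contradict the primary derivation for the same patient over the same days.

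**Working it through.** **Inputs**

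- T = RBC units transfused in the interval (SAP 4.2.1.1 and 4.2.2.1).
- B = baseline RBC units per 8 weeks (SAP 3.3), with B > 0.
- S = value under SAP 4.2.2.1 = -100 × T / B.
- R = value under SAP 4.2.1.1 = -100 × (T - B) / B = 100 - 100 × T / B.

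**Difference**

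S - R = -100T/B - (100 - 100T/B) = -100, for every T and every B > 0. A numerical check over B = 1 to 29 and T = 0 to 59 gave -100 throughout, apart from rounding error of about 1e-13. Because T cannot be negative, S cannot exceed 0.

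**Values with B = 4**

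| T (units) | R, per 4.2.1.1 | S, per 4.2.2.1 |
|---|---|---|
| 0 | 100% | 0% |
| 2 | 50% | -50% |
| 4 | 0% | -100% |
| 6 | -50% | -150% |

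**Effect on the reported statistics**

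SAP 3.2 calls for mean, median, SD, quartiles, minimum and maximum. A constant shift moves all of these by -100 points except the SD, which does not change. For illustration only, take five assumed patients with B = 4, 5, 6, 8, 10 and T = 0, 2, 3, 8, 12:

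- R = 100, 60, 50, 0, -20: mean 38.0, median 50, SD 48.2, range -20 to 100.
- S = 0, -40, -50, -100, -120: mean -62.0, median -50, SD 48.2, range -120 to 0.

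**Where the table meets the primary derivation head-on**

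The offset applies to both strata and all six rows. A direct contradiction with the primary endpoint needs the same patient and the same days.

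- Percent reduction is a response criterion for HTB only. For the other stratum the rule is "LTB: A patient is considered a responder if they are free of RBC transfusions over any continuous 8-week period".
- The primary rolling intervals are "Days 2-57, Days 3-58,..., Days 113-168". Start days 2 to 113 give 113 - 2 + 1 = 112 intervals.
- Two rows of the secondary table coincide with one of these: "Week 1 to 8 (Rel Day 2 to 57), Week 9 to 16 (Rel Day 58 to 113". The third row, Days 114 to 169, ends one day after the last rolling interval, and the other three rows lie after Week 24.

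In those two rows, an HTB patient-interval that meets the response rule has R between 50 and 100, so S falls between -50 and 0. With 4 baseline units and 2 interval units, the patient meets the primary criterion at +50% and appears at -50% in the secondary table.

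**The case against.** The strongest case on the other side is that this is a slip with little consequence. The label and the complete formula in 4.2.1.1 make the intent obvious. A programmer would notice at once that nobody can show a positive reduction. The table is descriptive, with no test or decision attached, and a constant shift can be undone by adding 100. The total-units summary in the same section conveys transfusion use without the formula. The formula also has no bearing on the transfusion-independence part of the endpoint. All of this stands, and it limits the weight of the point. It does not make the formula right: a program that follows the SAP gives wrong values, and one that corrects it departs from the SAP without a record.

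A second objection is that an equation can lose a term when a PDF is converted to text. That cannot be fully excluded. It is unlikely, because the fraction has a complete numerator, denominator and multiplier, and the neighbouring formula in 4.2.1.1 kept its subtraction. A look at the equation in the PDF settles it.

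A third is that the corrected formula still divides by zero when B = 0. This can happen, because strata are set on 16 weeks of history and B covers only the last 8. Both formulas are undefined in that case. It is a separate question, which this correction neither causes nor solves.

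**Conclusion.** The point holds. The percent-reduction formula in SAP 4.2.2.1 is wrong as written and conflicts with SAP 4.2.1.1. For every baseline above zero, in both strata and all six intervals, it gives a value exactly 100 percentage points too low. The head-on clash with the primary derivation is narrower: HTB patients in two of the six rows.

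The error is confined to the percent-reduction summary. The primary erythroid response (HI-E) and the total-units summary are unaffected. It should be corrected, but its consequence is minor. The size given assumes that the formula is programmed as printed, which the documents neither confirm nor rule out.

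**What to change.** In SAP 4.2.2.1, replace the formula with:

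-100 × (total RBC units in the interval - baseline RBC units per 8 weeks) / baseline RBC units per 8 weeks

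This matches SAP 4.2.1.1. Then check the program line that produces the table. If output was already produced under the printed formula, rerun the table; adding 100 to each location statistic serves as a check.

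The cost is one line of SAP text and one program check. It needs no new data and changes no other analysis. This correction does not require any other change to 4.2.2.1.

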7.2 Treatment Discontinuation/ Withdrawal from the Study

7.2.1 Treatment Discontinuation

Treatment discontinuation is defined as any patient who permanently stops receiving study drug. A patient should be discontinued from study treatment if, in the opinion of the Investigator or Sponsor, it is medically necessary, or if it is the wish of the patient.

Patients who prematurely discontinue study drug prior to 48 weeks of treatment will have an EOT (W48D1) visit performed at the time of discontinuation followed by the Safety Follow-up visit within 28 days.

Patients must be discontinued from treatment for any of the following reasons:

- An AE that requires permanent discontinuation of study treatment
- Withdrawal of consent by the patient
- Treatment interruption for > 28 days due to a related AE
- Lack of efficacy
- Disease progression
- Pregnancy
- Patient lost to follow-up
- Investigator decision
- Noncompliance to protocol
- Termination of the study by the Sponsor

44 of 77

AEs leading to the discontinuation of study drug will be followed for 28 days after administration of last dose of study drug or until resolution, resolution to baseline, or until the event is considered stable or chronic.

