(HI-E)		of 2 Hb measurements (apart from any transfusion) within 16 wk before			
		treatment onset			
	Low transfusion	Absence of any transfusions for at least 8 wk in an observation period of			
	burden (LTB)	16-24 wk with the same transfusion policy (defined below) compared with			
		16 wk prior to treatment			
	High	Major response: Transfusion independence, defined by the absence of any			
	transfusion	transfusions over a period of minimum 8 wk in an observation period of			
	burden (HTB)	16-24 wk with the same transfusion policy (defined below) compared with			
		16 wk prior to treatment			
		Minor response: Reduction by at least 50% of RBCs over a minimum of			
		16 wk with the same transfusion policy (defined below) compared with 16 wk			
		prior to treatment			
	On-treatment	Transfusion policy for the individual patient prior to therapy should be			
	RBC	maintained on treatment if not otherwise clinically indicated (documentation			
	transfusion	by the treating physician required); maximum variation between pre- and on-			
	policy	study practice of 1 g/dL (or 0.6 mmol/L) in terms of transfusion threshold			
-	se (pretreatment,	• Absolute increase of $30 \times 10^9/L$ for patients starting with $>20 \times 10^9/L$			
$<100 \times 109/L)$, HI-P	PLTs or			
		• Increase from $<20 \times 10^9/L$ to $>20 \times 10^9/L$ and by at least 100% In addition,			
		Evolution of bleeding symptoms is to be taken into account			
Neutrophil resp	nonse	At least 100% increase and an absolute increase >0.5 × 10 ⁹ /L			
	all patients), HI-N	(pretreatment, $<1.0 \times 10^9/L$)			
	relapse after HI				
l rogression or	reapse area in	For HI-N and HI-P:			
		At least 50% decrement from maximum response levels in			
		neutrophils or platelets, and not meet response criteria when			
		compared to baseline			
		For HI-E:			
		• Reduction in Hb by ≥ 1.5 g/dL, and not meet response criteria when			
		compared to baseline			
		Transfusion dependence			
		HTB: increase in transfusion burden by at least 50%			

Hb = hemoglobin; HI = hematologic improvement; PLTs = platelets; wk = week(s).

^{*}If patients received 1 or 2 RBC concentrates during the 16-wk pre-treatment period, it is recommended that HI-E achievement requires not only transfusion independence but also an increase of Hb by at least 1.5 g/dL (= 0.9 mmol/L).

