2. PATIENT POPULATION

2.1. Population Definitions

The following patient populations will be evaluated and used for presentation and analysis of the data:

- All Enrolled Patients: This is defined as all patients who signed the informed consent form.
- Full Analysis Set (FAS): All patients who signed the informed consent and received at least 1 dose of etavopivat.
- Safety Set: All patients who receive at least one dose of etavopivat (including partial dosing).
- Efficacy Evaluable Set (EES): All patients in the FAS who have completed the Week 24 Response visit and who have a baseline record of the primary endpoint.
- Pharmacokinetic Set: All Safety Set patients who have at least one evaluable concentration for etavopivat at a scheduled PK time point after the start of dosing. For patients with protocol violations or events with potential to affect the PK concentrations, a decision regarding inclusion in the analysis will be made on a case-by-case basis and documented as part of the DBL minutes.

The Efficacy Evaluable Set is the primary population for the analysis of efficacy parameters. The PK Set is the primary population for the analysis of PK parameters. The Safety Set is the primary population for the analysis of safety endpoints. The FAS is used for demography tables.

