3.3. Baseline Definitions

Baseline values for Hb will be defined as the mean of the screening and Day 1 pre-treatment values. If one of the two assessments is missing, then a single assessment prior to the start of study treatment will be defined as baseline.

History of RBC transfusions will be gathered for each patient for up to 16 weeks before start of study treatment. Baseline RBC transfusion burden units per 8 weeks will be defined as the summed units transfused in the 8 weeks up to pre-dose Day 1 (Rel Day -55 to 1).

For all other analyses, baseline will be defined as the most recent non-missing measurement prior to the first administration of study drug.

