4.2. Efficacy Evaluation

Efficacy analyses will be conducted using the EES.

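### The transfusion-burden table follows only patients still on treatment among Week 24 completers, so its reductions can be too favourable throughout and can rise after Week 24 with no patient improving

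*SAP*

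**What the plan says.** SAP section 4.2.2.1 covers LTB and HTB patients only. It summarises total RBC units and percent reduction from baseline in six consecutive 8-week intervals. Week 24 falls at the boundary between the third and fourth: "Week 17 to 24 (Rel Day 114 to 169), Week 25 to 32 (Rel Day 170 to 225". The inclusion rule is: "Patients who have discontinued treatment prior to completing the specified interval will be excluded from the analysis".

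Three other provisions decide who is in the table.

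- **Analysis set.** SAP section 4.2: "Efficacy analyses will be conducted using the EES". SAP section 2.1 defines that set as "All patients in the FAS who have completed the Week 24 Response visit and who have a baseline record of the primary endpoint".
- **Reasons to stop.** Protocol section 7.2.1 opens its list with "Patients must be discontinued from treatment for any of the following reasons". The list includes "Lack of efficacy", with no threshold or time point, and disease progression.
- **Missing data.** SAP section 3.9 makes no substitutions unless otherwise specified, and section 4.2.2.1 specifies none.

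The baseline for the percentage is a single 8-week count, the "summed units transfused in the 8 weeks up to pre-dose Day 1 (Rel Day -55 to 1"). Protocol Table 1-1 has transfusions recorded until the end-of-treatment visit or 8 weeks after the last dose, whichever is first. Section 7.2.1 places that visit at the time of discontinuation.

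**The concern.** A patient whose transfusion need does not fall is the patient most likely to be stopped for lack of efficacy. Progression can work the same way. Protocol Appendix A lists transfusion dependence under disease progression, and under progression or relapse after haematologic improvement it lists "HTB: increase in transfusion burden by at least 50" per cent. Section 7.2.1 does not say which definition applies, but both involve the quantity being summarised. Exclusion from an interval can therefore depend on the result for that interval.

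The rule also discards data already collected. A patient who stops on Day 50 has about seven weeks of recorded transfusions and contributes nothing to interval 1.

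Section 4.2.2 contains only this table, so it is the only planned secondary analysis of the retained endpoint on reduction in RBC transfusions. The Per-Protocol Set has been dropped (SAP section 5.2), and no sensitivity analysis in all treated patients is planned. Elsewhere the SAP treats early stoppers differently: in the informal futility assessment (section 3.11), patients who discontinue before their HI-E assessment is complete count as non-responders. Here they disappear. A reader could take a level, or a rise over time, produced by selection for a treatment effect.

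**Working it through.** The plan states no figure for this table, so there is none to reproduce. The check asks what the table would show if each patient's reduction stayed constant over the whole study.

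**Assumptions (none is in the documents)**

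- True percent reduction per patient is normal, mean 25, SD 30.
- In each 8-week interval a fraction *q* of patients with reduction below 20% stop, and 5% of the others stop.
- Reduction is 100 × (1 − units / baseline), the baseline-subtracting form of SAP section 4.2.1.1.

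**Step 1. Split the patients at 20%.**

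- z = (20 − 25) / 30 = −0.167; share below = Φ(z) = 0.434; share above = 0.566; density φ(z) = 0.393.
- Mean below = 25 − 30 × 0.393 / 0.434 = −2.2.
- Mean above = 25 + 30 × 0.393 / 0.566 = 45.8.

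**Step 2. Mean among those still on treatment after *k* intervals.**

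Mean(k) = [0.434 (1 − q)^k × (−2.2) + 0.566 × 0.95^k × 45.8] / [0.434 (1 − q)^k + 0.566 × 0.95^k]

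For q = 0.30 and k = 3 the weights are 0.149 and 0.485, giving 34.6. For k = 6 they are 0.051 and 0.416, giving 40.6.

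**Step 3. Apply the EES.** Anyone who stops before the Week 24 visit is absent from all six intervals. Intervals 1 to 3 therefore share essentially one fixed set of patients and all show Mean(3). The exclusion rule adds further selection only from interval 4. The small exception is a stop between the Week 24 visit (target Day 162) and Day 169.

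| Stopping per interval, below 20% vs others | Int. 1–3 | Int. 4 | Int. 5 | Int. 6 | True mean |
|---|---|---|---|---|---|
| 30% vs 5% | 34.6 | 37.0 | 39.0 | 40.6 | 25 |
| 15% vs 5% | 28.8 | 30.0 | 31.2 | 32.3 | 25 |
| 5% vs 5% | 25.0 | 25.0 | 25.0 | 25.0 | 25 |

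In the first row the excess is 34.6 − 25 = 9.6 points before Week 24, and the rise after it is 40.6 − 34.6 = 6.0 points. In the second row they are 3.8 and 3.5.

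**Step 4. Does it need an average benefit?** Simulations with no average treatment benefit were also run, with the EES applied. They assumed Poisson counts, true means of 2.5 (LTB) and 6 (HTB) units per 8 weeks, and 30% stopping per interval among patients with no reduction, plus 3% at random.

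- Lasting differences between patients, averaging zero change: 14, 14, 14, 17, 19, 22 if stopping follows the same interval's result; 12, 11, 6, 8, 11, 14 if it follows the previous interval's.
- Constant true rates with a noisy 8-week baseline, same-interval stopping: 1, 2, 1, 6, 10, 13, against a flat −19 without selective stopping.
- Every patient exactly at baseline: 0 throughout.
- Pure interval-to-interval noise around each patient's own baseline: no growth (a flat 7, or 7, 8, 0, 0, 0, 0).

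So a rise needs stopping to track something that lasts: real differences between patients, or error in the baseline count.

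**The case against.** - **No steady climb from Week 1.** A reader might infer that the reductions must grow across all six intervals even if nobody improves. The documents do not support that. The EES fixes the patient set for intervals 1 to 3, so dropout can produce a rise only after Week 24; before that it is a level shift. Nor is the rise certain, as the last two cases in step 4 show. This stands.
- **The level shift belongs to the EES.** The excess in intervals 1 to 3 comes from the Week 24 completer restriction, not from the sentence in section 4.2.2.1. Correct as attribution, but both rules act on this table and a reader sees their joint effect.
- **The stopping rates are assumed.** The protocol gives no rate and no definition of lack of efficacy. The SAP was written after the decision to terminate early, and section 4.1.1 codes such stops as termination by the sponsor. Those need not depend on response, and if most stops are of that kind the bias may be small. This stands, and it is why a range is shown.
- **Attrition will be visible.** SAP section 3.2 reports the number of patients, section 4.1.1 tabulates discontinuation reasons by treatment period, and the listings hold all recorded data. True, but a visible count does not correct a mean.
- **The table is descriptive.** It carries no test or decision rule, and transfusions also enter the primary endpoint through the LTB and HTB response rules. This limits the consequence. It does not make the table a fair estimate of reduction in treated patients.

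**Conclusion.** The concern holds in limited form. The table describes patients selected partly on the outcome it reports and leaves out recorded transfusions. Its reductions can be too favourable in all intervals and can rise further in intervals 4 to 6 with no patient improving. Under the assumed rates the overstatement is about 4 to 10 points in intervals 1 to 3 and about 7 to 16 points by interval 6; it is zero if stopping is unrelated to response. Only the direction, and the fact that growth can start only after Week 24, are robust. The sizes are illustrative. With about 15 patients planned per stratum, a few exclusions can move a mean.

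All percentages here presume that the reduction formula subtracts baseline. The formula printed in section 4.2.2.1 does not, so an unchanged patient would score −100%. That needs its own correction.

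The last interval also needs clarifying. It ends on Day 337, but SAP Table 3 places the Week 48 visit at Day 330 (window 327 to 333). Read literally, the rule could remove patients who completed 48 weeks.

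**What to change.** 1. Add one whole-treatment row for all treated LTB and HTB patients (FAS), by stratum. For each patient give RBC units / observed days × 56, from Day 2 to the last day of transfusion recording, and the percent reduction of that rate from the 8-week baseline. Make it the main summary of this endpoint. It removes both the interval exclusion and the Week 24 completer restriction, and it uses data already collected.
2. Keep the by-interval table, with a title or footnote stating that it describes Week 24 completers still on treatment at the end of each interval.
3. Optionally include partial intervals with at least 28 observed days, as units / observed days × 56. This recovers discarded data but does not remove selection: a patient who stops in one interval is still missing from those after it.

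The cost is minor programming. The downside is that rates from short observation are noisier, so observed days should be shown beside the rate.
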